Title:

A Pilot Study of F-18 Fluciclovine-PET/CT as A Diagnostic Tool for Bone Metastases in Patients With Hormonal Sensitive and Resistant Prostate Adenocarcinoma

Co-Investigators: [name], PhD, Medical Imaging

[name], Medicine

Sub-investigators: [name], Urology

[name], Radiation Oncology

[name], Medicine

[name], Medical Imaging

[name], PhD, Medical Imaging

Version Date 06/04/2020

Background:

Approximately one-third of men treated for primary prostate cancer (PC) will have biochemical recurrence (BCR) of prostate cancer within 10 - 15 years after initial treatment. Approximately one-third of men with BCR will develop metastatic disease within 8 years. Thus, determining the location of the recurrence is critical, since it guides the optimal choice of therapy. In other words, treating all men with BCR for potential metastatic disease would result in overtreatment of two-thirds. However, knowledge of the location of the disease for those patients who do develop recurrence and metastasis can direct salvage surgical or radiation therapy. Biochemical recurrence is most often detected through the blood test for prostate specific antigen (PSA). While the blood test can detect early recurrence, it is severely limited since it cannot localize the site of disease recurrence. Approximately 90% of the standard battery of imaging tests, including computed tomography (CT), magnetic resonance imaging (MRI) and bone scintigraphy, may be negative at the time of detection of BCR when PSA levels are still low and hence a new more effective detection modality is needed.

In 2016, a new positron emission tomography (PET) radiopharmaceutical was approved by the United States Food and Drug Administration for localizing BCR in prostate cancer. This new radiopharmaceutical, F-18 fluciclovine, is like amino acids which are the building blocks of proteins. When F-18 fluciclovine is injected into the bloodstream of a patient, prostate cancer cells accumulate F-18 fluciclovine, and then a PET/CT scanner is used to localize the fluciclovine and thus the cancer. This detection modality proved to be effective and safe.

Significance:

F-18 fluciclovine gained approval from strong data which accurately correlated imaging with biopsy results; however, only a small number of those biopsies were from bone. Thus, there is a need for more data on the accuracy of F-18 fluciclovine with regards to PC spreading to the bone. In addition, we see on average 180-200 patients with prostate cancer per year and hence we can accrue well for this trial.

Study Hypothesis:

1. Validation by core needle biopsy of suspected osseous metastases identified on F-18 fluciclovine-PET/CT in patients with castrate resistant prostate cancer (CRPC) in need for biopsy for molecular testing.
2. Correlate the results of blood cell free DNA mutational analysis, tissue mutational testing of the biopsy material, and results of the F-18 fluciclovine-PET/CT (standardized uptake value (SUV) of lesions and extent of disease). This can assist with the identification of targetable mutations in the future for approved drugs in prostate cancer. For example, olaparib is currently approved for the treatment of prostate adenocarcinoma harboring the following mutations: BRCA1/BRCA2/PALB2/FANCA/CHK2/ATM. This secondary aim is exploratory.

Methods:

The study will consist of prostate cancer patients who would not ordinarily obtain an Axumin-PET scan for routine standard of care but have a need for bone biopsy. This will include patients with metastatic castrate resistant prostate cancer. The current standard of care is to obtain molecular testing for patients with prostate cancer castrate resistant disease for BRCA1, BRCA2, PALB2, CHK2, FANCA, and ATM as olaparib is approved for these patients after progression on chemotherapy and targeted drugs [2]. Moreover, the FDA recently approved pembrolizumab for patients with MSI-H solid tumor, which includes patients with prostate cancer, after a clinical trial showed robust results for these patients [3]. Hence, molecular testing is recommended as part of standard of care therapy for these patients due to FDA approved drugs that can provide clinical benefit for patients.

Moreover, since PC most commonly metastasizes to the bone, most of the attained biopsied specimens are from the bone. This reflects current standard of care (SOC) therapy in GU-oncology clinics. cfDNA testing (Guardant360) is used as SOC therapy in clinics to obtain potential targetable mutations, for clinical trial participation, for patients with castrate resistant prostate cancer who have been treated with SOC therapy and their disease is still progressing.

The trial will obtain correlative F-18 fluciclovine-PET/CT imaging and bone biopsy results on a total of 15 patients with prostate cancer. Patients with negative biopsies will be followed for minimum of another 12 months (SOC imaging and clinical assessment) for possibility of false negative biopsy. We will review medical records at 12 months post bone biopsy.

As standard of care, mutational analyses of the biopsy material (CARISx) and blood cell free DNA (Guardant360) will be obtained. These results will also be compared with SUV of lesions and extent of disease as potential imaging biomarkers of certain mutations or disease aggressiveness.

Statistical Considerations:

The study will calculate sensitivity, specificity, true positive and false positive rate of positive bone findings on F-18 fluciclovine-PET/CT scan compared to gold standard of bone biopsy. The study will also estimate the differences in the SUV parameters using a 95% confidence interval.

Risk to Participants:

Subjects are going to have bone biopsies as standard of care, therefore there is no additional risk being a participant in this study.

Subjects will receive the additional radiation from the non-standard of care F-18 fluciclovine-PET/CT scan.

PET/CT scan: A PET/CT scan with F-18 fluciclovine injection is a nuclear imaging test that scans the body from head to thigh and detects cancer. The risks to the subject associated with PET/CT scans that are part of normal cancer care are small. A radiotracer chemical is used in PET/CT scans; the amount of radiation the subject is exposed to is low and is considered so small that it does not affect the normal processes of the body. There is a rare risk of a major allergic reaction to the radiotracer.

Number of patients whose PET images will be analyzed:

15 men .

Data and Safety Monitoring Plan:

1. Identification of the DSMB obligated for oversight responsibilities:

The University of Arizona Cancer Center Data and Safety Monitoring Board (DSMB) will provide ongoing oversight for this trial. This study has been assigned a Low Risk level by the DSMB.

2. Identification of the entity obligated for routine monitoring duties:

Routine monitoring will be provided by the Quality Assurance/Quality Control (QA/QC) Program to ensure that the investigation is conducted according to protocol design and regulatory requirements.

This trial will also undergo real-time monitoring by the PI and study team, including documentation of real-time monitoring of any new or ongoing safety issues.

The trial will have a AE/SAE log that will be reviewed and signed by the PI in a timely manner of the knowledge and documentation of an AE occurring. SAEs will be reviewed within 24 hours of notification of event.

3. Monitoring progress and data review process:

Routine monitoring of subject data will be conducted at least quarterly.

The first routine monitoring visit will include at a minimum:

- Informed consent – 50% of cases enrolled;
- Subject eligibility – 10% of cases, up to two subjects;
- Data review – 10% of cases, up to two subjects.

All subsequent monitoring visits will consist of randomly selected subject cases based on current enrollment and include continuing review of previously selected cases, as applicable.

A monitoring visit report and follow-up letter will be completed approximately two weeks after the routine monitoring visit; a copy will be maintained in the study file. The monitor will request additional source documentation, clarification, information, or corrections to the CRF and/or regulatory records from the Clinical Research Coordinator (CRC) or other applicable staff responsible for the study and resolution of queries/findings. Documentation of such a request will be maintained with a copy of the monitor's visit report for follow-up at the next monitoring visit. Electronic records will be available in the institutional database or provided by the QA/QC Program staff.

The Principal Investigator will ensure the accuracy, completeness, legibility and timeliness of the data reported in the Case Report Form (CRF), or other acceptable data formats. Source documentation supporting the study data should indicate the subject's participation in the trial and should document the dates and details of study procedures, adverse events, and patient status.

Case report forms, which include the inclusion/exclusion criteria form, adverse event forms and serious adverse event forms *[other forms, depending on study]* should be completed via the institution database or other acceptable data formats. Trials using paper CRFs will have the data entered with a black ball-point pen or typed. Corrections to the forms should not obscure the original entry and should be made by striking the incorrect information with a single line. Each strike should be accompanied by the initials of the corrector and the correction date. All subject forms and study files will be stored in a secure area limited to authorized staff.

Note: Routine monitoring of regulatory documents will be conducted at least annually.

4. Process to implement study closure when significant risks or benefits are identified:

We do not anticipate any additional significant risks or benefits associated with the research. If there is a reason to close the study before the planned study end, there are no additional risks to the subjects for sudden withdrawal. The subject care would continue with the standard of care plan in the event we closed the study due to any newly identified significant information.

5. Description of adverse events and reporting procedures:

ADVERSE EVENTS: An adverse event (AE) is any untoward medical occurrence in a patient or clinical investigation subject administered a pharmaceutical product and that does not necessarily have a causal relationship with this treatment. An AE can therefore be any unfavorable and unintended sign, symptom, or disease temporally associated with the use of a medicinal (investigational) product, whether or not related to the medicinal (investigational) product.

Any and all adverse events will be recorded on the UACC adverse events record form and reviewed by the Principal Investigator.

All adverse events will be classified using either the MedDRA term or NCI Common Terminology Criteria for Adverse Events (CTCAE) version 4.0 and will address:

- Grade
- Relationship to study drug (not related, unlikely, possible, probable, definitely)
- Causality other than study drug (disease related, concomitant medication related, intercurrent illness, other)
- Date of onset, date of resolution
- Frequency of event (single, intermittent, continuous)
- Event outcome (resolved, ongoing, death)
- Action taken (none, held, dose reduced, discontinued, medication given)

SERIOUS ADVERSE EVENTS: A serious adverse event (SAE) is any untoward medical occurrence that at any dose:

- a) Results in death;
- b) Is life-threatening;
- c) Requires in-patient hospitalization or prolongation of an existing hospital stay;
- d) Results in disability persistent or significant disability/incapacity, or:
- e) Is a congenital anomaly/birth defect.

Note: A SAE may also be an important medical event, in the view of the investigator that requires medical or surgical intervention to prevent one of the outcomes listed above.

All serious adverse events, regardless of attribution, and any deaths will be reported within 24 hours of notification of the event to the sponsor and, if applicable, any collaborating entity. All serious adverse events and any deaths will be reported to the DSMB and to the University of Arizona Human Subjects Protection Program per the guidelines set forth in University of Arizona Cancer Center Data and Safety Monitoring Board Charter, Table 5: Adverse Event Reporting.

All submitted serious adverse events will be processed by the DSMB Coordinator monthly for initial trend analysis and then reviewed by the DSMB Chair. The assigned QA/QC Monitor will review the SAE reporting process to confirm reporting requirements are met.

6. Plan for assuring data accuracy and protocol compliance:

Routine study activity and safety information will be reported to the DSMB on a quarterly basis, or more frequently if requested. These reports will include:

- Study activity, cumulative and for the period under review;
- Safety (narrative description on non-serious and serious adverse events, protocol pre-determined early stopping rules for safety or treatment-emergent adverse events);
- Predetermined protocol early stopping rules for efficacy/futility;
- Status of study in relationship to stopping rules;
- Current dose level of study agent;
- Routine monitoring and protocol compliance (describe the monitoring process and identify the status of the monitoring);
- Comments;
- Attachments (AE data reviewed by the PI to compile the report, SAE letters and reports, results of any review(s), applicable correspondence with the IRB or other regulatory agencies)

Data, safety and study progress will be reported to:

- Human Subjects Protection Program (IRB) at least annually;
- Sponsor (if applicable) at least annually.

7. Identification of the sponsor or funding agency, as applicable:

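### The accuracy measures have no denominators: two of the four either repeat the other two or are predictive values under the wrong label, and the PPV that matches Hypothesis 1 is not named

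*Combined protocol and SAP*

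**What the plan says.** The accuracy analysis is set out in one sentence of Statistical Considerations, which takes the biopsy result as the reference: "The study will calculate sensitivity, specificity, true positive and false positive rate of positive bone findings on F-18 fluciclovine-PET/CT scan". No numerator, denominator or unit of analysis (patient or lesion) is given for any measure. The only confidence interval in that section is for another quantity: "The study will also estimate the differences in the SUV parameters using a 95% confidence interval".

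Study Hypothesis, item 1, states the question to be answered: "Validation by core needle biopsy of suspected osseous metastases identified on F-18 fluciclovine-PET/CT". PPV is not named anywhere in the document.

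Methods sets the size: "bone biopsy results on a total of 15 patients with prostate cancer". It also provides that "Patients with negative biopsies will be followed for minimum of another 12 months (SOC imaging and clinical assessment) for possibility of false negative biopsy".

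**The concern.** Hypothesis 1 starts from lesions that PET has already called suspicious and asks whether the needle confirms them. That is the probability of a positive biopsy given a positive PET, which is the PPV. Sensitivity and specificity condition the other way, on the biopsy result. On standard definitions the two remaining listed measures do so as well, because they are the same quantities under other names.

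With no formula written down, one printed false positive rate could mean the share of biopsy-negative cases that PET called positive, or the share of PET-positive cases that biopsy did not confirm. Either could be reported as following the plan, and the choice could be made after the 15 results are known. A reader could then take one figure for the other.

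**Working it through.** **Inputs.** The list of measures and the biopsy reference come from Statistical Considerations, the question from Study Hypothesis item 1, and N = 15 from Methods. The plan gives no expected accuracy, prevalence or sample-size derivation, so it has no figure to reproduce. All cell counts below are assumed. The biopsy result is taken at face value; follow-up of negative biopsies could move a case between cells but does not change the definitions.

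**Step 1: standard definitions.**
- Sensitivity = TP/(TP+FN); true positive rate = TP/(TP+FN). Identical.
- Specificity = TN/(TN+FP); false positive rate = FP/(FP+TN) = 1 − specificity.
- PPV = TP/(TP+FP); its complement = FP/(TP+FP).

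The identities follow from the algebra. Listing every 15-patient 2x2 table with at least one biopsy-positive and one biopsy-negative case gives 784 tables, with no exception.

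**Step 2: PPV is not fixed by sensitivity and specificity.** Hold both at 0.667 with N = 15 and vary the number of biopsy-positive patients:
- 3 biopsy-positive: TP 2, FP 4, PPV 2/6 = 0.33
- 6 biopsy-positive: TP 4, FP 3, PPV 4/7 = 0.57
- 9 biopsy-positive: TP 6, FP 2, PPV 6/8 = 0.75
- 12 biopsy-positive: TP 8, FP 1, PPV 8/9 = 0.89

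**Step 3: the two readings of the same labels** (assumed tables, N = 15).

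| TP/FP/FN/TN | True positive rate, standard | PPV | False positive rate, standard | Share of PET-positive not confirmed |
|---|---|---|---|---|
| 8/1/2/4 | 8/10 = 80% | 8/9 = 89% | 1/5 = 20% | 1/9 = 11% |
| 4/2/1/8 | 4/5 = 80% | 4/6 = 67% | 2/10 = 20% | 2/6 = 33% |
| 12/2/0/1 | 12/12 = 100% | 12/14 = 86% | 2/3 = 67% | 2/14 = 14% |

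For the false positive rate, the second reading is lower by 9 points in the first table, higher by 13 in the second, and lower by 52 in the third (66.7 − 14.3 = 52.4). The first two tables have the same sensitivity and specificity (0.80 each) but different PPVs.

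**Step 4: precision of a PPV.** If all 15 patients were PET-positive, exact (Clopper-Pearson) 95% intervals would be 38% to 88% for 10/15, 52% to 96% for 12/15, and 68% to 99.8% for 14/15.

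**Step 5: if only PET-positive sites are biopsied.** Then FN = TN = 0. Sensitivity = TP/TP = 100% and specificity = 0/FP = 0%, whatever the scanner does (each provided its denominator is not zero). With 12/3/0/0, PPV = 12/15 = 80% is the only informative figure. The documents do not say whether PET-negative sites are sampled.

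**The case against.** The strongest reply is that the plan may already include PPV. The sentence attaches the last two terms to positive bone findings on the scan, so PET-positive findings are a natural denominator. Listing sensitivity and specificity separately also suggests that the authors meant something different by the other two. A reader might infer from the standard definitions that the plan never computes PPV; the documents do not support that, because they define no measure and leave this reading open. What remains is that PPV would then appear under a label that conventionally means something else.

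Hypothesis 1 also names no metric, and the Significance section speaks more broadly of accuracy in bone, which sensitivity and specificity address too. That is fair: the match to PPV is an inference, though a close one, since the hypothesis starts from lesions found on PET.

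A reader might take the 52-point gap as the size of the problem, or assume that only a handful of men will be biopsy-negative. Neither is supported. The documents give no expected counts, and other assumed tables give 9 or 13 points, in opposite directions.

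A reader might also suppose that the consequence is the same however biopsy sites are chosen. The algebra is the same wherever the denominators are not zero, but the consequence is not. Sampling only PET-positive sites makes sensitivity and specificity uninformative, and relabelling does not cure that.

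Finally, PPV can be calculated from the same 2x2 counts, so no data are lost. This limits the harm; it also means that the remedy is cheap.

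**Conclusion.** The point holds as a gap in definition, not in data collection. On the standard reading, two measures are duplicates and the one that matches Hypothesis 1 is not explicitly planned. On the alternative reading, PPV and its complement are intended but mislabelled. Either way the sentence needs to change. The numerical effect depends on unknown counts: in the three assumed tables the two readings of the false positive rate differ by 9, 13 and 52 points, not always in the same direction. The conclusion rests on standard definitions and on reading Hypothesis 1 as conditional on a positive PET. It does not rest on any of the assumed tables.

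**What to change.** In Statistical Considerations:
- Replace the true positive and false positive terms with positive predictive value (biopsy-positive among PET-positive biopsied) and its complement.
- Make PPV the lead estimate for Hypothesis 1, with an exact 95% confidence interval.
- State one unit of analysis, patient or lesion, and use it throughout.
- Report the four cells of the 2x2 table, and n/N for every measure.
- State that, if only PET-positive sites are biopsied, sensitivity (100%) and specificity (0%) are fixed by construction and will not be interpreted.

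The cost is a few lines of text. No new patients, data or procedures are needed.

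### Sensitivity and specificity against biopsy are promised, but both are fixed in advance if only PET-positive sites are biopsied, and the documents do not say how the biopsied site relates to the PET call

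*Combined protocol and SAP*

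**What the plan says.** All references are to the combined protocol and SAP.

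- **Purpose (Significance):** "there is a need for more data on the accuracy of F-18 fluciclovine with regards to PC spreading to the bone".
- **Accuracy analysis (Statistical Considerations):** the study will "calculate sensitivity, specificity, true positive and false positive rate of positive bone findings on F-18 fluciclovine-PET/CT scan", with bone biopsy as the reference. This is the only accuracy analysis in the document.
- **What is biopsied (Study Hypothesis, item 1):** "Validation by core needle biopsy of suspected osseous metastases identified on F-18 fluciclovine-PET/CT".
- **Who enters (Methods):** men who "would not ordinarily obtain an Axumin-PET scan for routine standard of care but have a need for bone biopsy". Risk to Participants adds: "Subjects are going to have bone biopsies as standard of care".
- **Numbers (Methods):** "The trial will obtain correlative F-18 fluciclovine-PET/CT imaging and bone biopsy results on a total of 15 patients with prostate cancer".
- **Follow-up (Methods):** "Patients with negative biopsies will be followed for minimum of another 12 months", to allow for a falsely negative biopsy, and then "We will review medical records at 12 months post bone biopsy". The second sentence does not say which men it covers.

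No section gives a rule for choosing the biopsy site, the order of scan and biopsy, or the unit of analysis (man or lesion). None gives a reference result for PET-negative bone that is not biopsied.

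**The concern.** Sensitivity and specificity need reference results at PET-negative as well as PET-positive sites. The hypothesis points to PET-positive targets only. The entry and risk wording points to biopsies that would happen anyway, possibly at a site chosen without PET. The two strands lead to different tables, and the analysis sentence does not separate them.

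At stake is what the trial can say about its stated purpose. If the hypothesis is followed literally, two of the named measures carry no information about the scan. If some PET-negative sites are biopsied, the measures describe biopsied sites only and may be biased. The remaining terms, the true and false positive rates, do not settle the matter. They could mean the positive predictive value (PPV) and its complement, or they could repeat sensitivity and one minus specificity.

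**Working it through.** **Inputs.** From the documents: 15 men, biopsy as the reference, the measures named above. The plan gives no expected accuracy, no share of biopsies expected to be malignant and no basis for the 15, so there is no figure of its own to reproduce. One biopsied site per man is assumed below.

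**Step 1. Every biopsied site is PET-positive.** With no PET-negative row, FN = TN = 0. Then sensitivity = TP/(TP + 0) = 100% and specificity = 0/(0 + FP) = 0%, or 0/0 if FP = 0. Only the PPV, TP/(TP + FP), varies with the data (Clopper-Pearson 95% intervals):

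| Biopsy positive / negative | Sensitivity | Specificity | PPV (exact 95% CI) |
|---|---|---|---|
| 15 / 0 | 100% | undefined | 100% (78.2–100) |
| 14 / 1 | 100% | 0% | 93.3% (68.1–99.8) |
| 12 / 3 | 100% | 0% | 80.0% (51.9–95.7) |
| 10 / 5 | 100% | 0% | 66.7% (38.4–88.2) |
| 8 / 7 | 100% | 0% | 53.3% (26.6–78.7) |

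**Step 2. Effect of the 12-month follow-up in that case.** A biopsy-negative man is a false positive. Reclassifying him can only move him to true positive. Starting from 12/15, reclassifying all three negatives moves the PPV from 80.0% to 15/15 = 100%. Sensitivity stays at 100%, and specificity stays at 0/FP or becomes 0/0.

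**Step 3. Some biopsied sites are PET-negative, but PET-positive sites are preferred.** Let v be the chance that a PET-negative site is biopsied, relative to a PET-positive site. Assume that, given the PET call, the choice of site does not depend on disease. At site level:

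- reported sensitivity = Se / (Se + v(1 − Se))
- reported specificity = v·Sp / (v·Sp + 1 − Sp)

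For Se = 0.70, Sp = 0.80 and v = 0.25: 0.70/(0.70 + 0.075) = 90.3%, and 0.20/(0.20 + 0.20) = 50.0%. All values of Se, Sp and v are assumptions; a range follows (reported sensitivity / specificity):

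| Assumed true Se/Sp | v = 0.1 | v = 0.25 | v = 0.5 | v = 1 |
|---|---|---|---|---|
| 70% / 80% | 95.9 / 28.6 | 90.3 / 50.0 | 82.4 / 66.7 | 70 / 80 |
| 80% / 80% | 97.6 / 28.6 | 94.1 / 50.0 | 88.9 / 66.7 | 80 / 80 |
| 90% / 70% | 98.9 / 18.9 | 97.3 / 36.8 | 94.7 / 53.8 | 90 / 70 |

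For any v below 1 and imperfect accuracy, sensitivity rises and specificity falls. The size depends on v, which the documents do not give.

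**Step 4. The site is chosen without regard to PET, or the man has only one candidate site.** Then v = 1 and PET-guided selection adds no bias. Both measures are valid among biopsied sites, but do not describe bone that was not biopsied.

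**The case against.** The strongest reply is that these men need a bone biopsy whatever the scan shows, and that PET and biopsy results are promised on all 15. A PET-negative man could therefore be biopsied and fill the PET-negative row. This stands. A reader might infer that the planned sensitivity and specificity are certain to be artefacts; the documents do not support that, because only the hypothesis wording points to PET-positive targets alone. Equally, nothing in the documents rules that case out.

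A reader might also infer that targeting PET-positive sites always biases the result, or that the sizes in Step 3 apply to this trial. Neither follows. With one candidate site per man there is no choice to bias. Step 3 is also a site-level calculation. If the man is the unit, all 15 have a biopsy, so partial verification of sites does not describe that analysis and its percentages cannot be carried over.

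The trial is a pilot with no decision rule. That excuses wide intervals, but it does not excuse a measure whose value may be set by the design; enrolling more men would not change Step 1.

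Nor does the follow-up supply the missing reference. It is aimed at biopsy-negative men and at falsely negative biopsies. The record-review sentence is not said to verify PET-negative bone.

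**Conclusion.** The concern holds in a conditional form. If Hypothesis 1 is followed and every biopsied site is PET-positive, sensitivity is 100% and specificity 0% or undefined. That is arithmetic and, given at least one positive biopsy, needs no assumed accuracy. If some biopsied sites are PET-negative, the two measures apply to biopsied sites only. At site level, sensitivity is biased upward and specificity downward where PET-positive sites are preferred in men with more than one candidate site. The direction does not depend on the assumed accuracies; the size does, along with the assumed verification ratio.

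The documents do not show which situation applies or what the unit is. Confidence is high that the rule is missing and that Step 1 is right. It is not high for any particular amount of bias.

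The wide PPV intervals should not be over-read either. A reader might infer from the lower limit of 78.2% at 15/15 that 15 lesions could never exclude a PPV of 80%, but 8/15 (26.6% to 78.7%) would exclude it from below.

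**What to change.** In Statistical Considerations:

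1. Make the main measure the PPV of PET-positive biopsied bone lesions, one index lesion per man, with an exact 95% confidence interval. Give it by biopsy alone and again after the 12-month follow-up. Use it to define the true and false positive rates now named. One lesion per man is this review's choice of unit; the plan states none.
2. Record the PET call at the biopsied site without knowledge of the pathology, and record whether PET was used to choose the site.
3. Report the 2×2 counts. If no biopsied site is PET-negative, give no sensitivity or specificity. Otherwise give both with exact 95% confidence intervals, labelled *among biopsied sites*. Add *subject to verification bias* only where PET guided the choice of site.

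**Cost.** Analysis wording and one recorded PET call per biopsied site; no extra men, scans or biopsies. The PET read must be made without knowledge of pathology, which needs some organisation because the order of scan and biopsy is not stated. The trial also gives up any claim to overall sensitivity or specificity for bone metastases. PPV does not replace that claim: it says nothing about missed disease, and it depends on how many biopsied sites are malignant. For an assumed 70%/80% scan, PPV = 0.70p/(0.70p + 0.20(1 − p)), which is 84.0%, 93.3% and 96.9% at p = 60%, 80% and 90% malignant.

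### Does the loosely worded 95% interval for SUV differences, with no stated role for the 12-month follow-up, need a change to the plan?

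*Combined protocol and SAP*

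**What the plan says.** Statistical Considerations has two sentences. The first plans accuracy measures for PET bone findings, "compared to gold standard of bone biopsy", with no interval. The second reads "The study will also estimate the differences in the SUV parameters using a 95% confidence interval". It is the only confidence interval in the document, and no SUV parameter, pair of groups or unit of analysis is named there or elsewhere.

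Methods adds two relevant points.

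- On follow-up: "Patients with negative biopsies will be followed for minimum of another 12 months (SOC imaging and clinical assessment) for possibility of false negative biopsy". Records are reviewed 12 months after the biopsy. No sentence says what the review does to a man's classification.
- On sequencing: "mutational analyses of the biopsy material (CARISx) and blood cell free DNA (Guardant360) will be obtained", and then "These results will also be compared with SUV of lesions and extent of disease as potential imaging biomarkers of certain mutations or disease aggressiveness". This is the only SUV comparison the document describes. Study Hypothesis, item 2, sets the same aim and says of it: "This secondary aim is exploratory".

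On the population, Study Hypothesis, item 1, speaks of validation "in patients with castrate resistant prostate cancer (CRPC) in need for biopsy for molecular testing", and Methods says "This will include patients with metastatic castrate resistant prostate cancer". The title also names hormone-sensitive disease.

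**The concern.** Two analysts given the SUV sentence alone could compute different intervals. They might choose different SUV measures, group by biopsy result or by mutation status, and count men or lesions. If the choice came after the SUVs were seen, it could be steered by them.

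The groups also look unsettled under each natural reading.

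- **By biopsy result.** Biopsy is the reference standard, yet the plan expects that some biopsies may be falsely negative. A man whose biopsied site later proves metastatic would stay in the negative group if biopsy alone decides, and would dilute the SUV difference. The biopsied lesions are those suspected on PET, so negatives may be few and one man may carry much weight.
- **By tissue mutation status.** A core without tumour may give no tumour sequence. Counting such a man as a non-carrier would create an SUV difference where mutation has no effect.

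At stake is the size of one descriptive estimate. The plan attaches no test, decision rule or treatment choice to it.

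**Working it through.** **Inputs.** From the documents: 15 men, a 95% interval, bone biopsy as reference, and at least 12 months of follow-up for negatives. The documents give no SUV spread, expected SUV difference, number of negative biopsies, false-negative rate or carrier rate, so there is no planned figure to reproduce. Everything below rests on assumed values, with ranges. Let d be the true SUV difference in per-man standard deviations (SD), with one value per man.

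**1. Is there a contradiction?** The reference standard fixes who is biopsy-negative: the man whose biopsy is negative. The follow-up sentence asks whether that biopsy missed tumour. The two are compatible. What is missing is a rule for final status after follow-up.

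**2. Dilution if the contrast were by biopsy result.** Suppose one of k negatives is falsely negative, with uptake a fraction f of the way from the true negatives to the positives. Then

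expected difference = d × (1 − f/k).

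| k negatives | f = 1 | f = 0.5 | f = 0 |
|---|---|---|---|
| 2 | 0.50d | 0.75d | d |
| 3 | 0.67d | 0.83d | d |
| 4 | 0.75d | 0.875d | d |
| 5 | 0.80d | 0.90d | d |

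A simulation at k = 3, f = 1 gives 0.666d, which agrees. The loss at k = 3 therefore runs from a third to nothing, depending on an uptake value nobody has.

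**3. Coverage at 12 vs 3 with one false negative** (normal data, equal spread, pooled t-interval), for d = 1, 2, 3:

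- f = 1: 0.928, 0.880, 0.819.
- f = 0.5: 0.945, 0.929, 0.908.

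**4. Shift against precision.** Half-width in observed pooled SDs = t(0.975, 13) × √(1/n₁ + 1/n₂), with t = 2.160:

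- 8 vs 7: 2.160 × √(1/8 + 1/7) = 1.118.
- 12 vs 3: 2.160 × √(1/12 + 1/3) = 1.395.
- 13 vs 2: 2.160 × √(1/13 + 1/2) = 1.641.

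The last two are not directly comparable, because a false negative left among the negatives inflates the observed SD. In true SDs, the simulated mean half-width at 12 vs 3 is 1.40, 1.50 and 1.66 for d = 1, 2, 3, against 1.61 after moving the man (13 vs 2). Moving him widens the interval at d = 1 and 2 and narrows it at d = 3.

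The shift at f = 1 is d/3, that is 0.33, 0.67 and 1.00. As a share of the half-width this is 0.33/1.40 = 24%, 0.67/1.50 = 45% and 1.00/1.66 = 60%. Even in the worst uptake case the shift stays inside the interval's own uncertainty.

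**5. Tissue mutation contrast.** Assume 3 carriers and no mutation effect. Counting u unsequenced biopsy-negative men as non-carriers gives an expected difference of u/(15 − 3) × d:

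- u = 2: 2/12 = 0.17d.
- u = 3: 3/12 = 0.25d.
- u = 5: 5/12 = 0.42d.

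Simulated for u = 3 and 5 with d = 1 and 2, the interval still covers zero 93% to 96% of the time. Leaving these men out removes the bias, with half-widths of 1.449 (10 vs 3), 1.485 (9 vs 3) and 1.591 (7 vs 3) observed SDs. Under a mutation grouping the dilution in step 2 does not arise.

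**The case for a change.** The strongest case for acting is that the plan itself promises this interval, so pilot status does not excuse leaving it undefined. A few lines of text would settle the measure, the contrast and the unit before SUVs are read against pathology. The 12-month record review is already planned, so no new visit or test is needed. PET-directed biopsy makes a small negative group likely, which is where one man's class counts most.

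The omission is real, and the arithmetic is correct under its assumptions. Three things weigh against requiring a change.

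- The harm comes from choices the plan does not make. It states no SUV contrast by biopsy result, and nothing in it suggests that men without a sequence would be classed as non-carriers.
- The sensible choices are easy to see. A follow-up gathered expressly to detect false-negative biopsies would be used when the results are written up, and a missing sequence would be treated as missing.
- A fixed rule has weaknesses of its own. The reclassified result waits 12 months. Follow-up cannot separate a missed tumour from one that appeared later. If the negative group's SD were twice the positives', the pooled t-interval would cover only 0.81 at 12 vs 3 and 0.76 at 13 vs 2, so a written rule does not secure the nominal level with groups this small.

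Whether hormone-sensitive men are enrolled, given the title and Study Hypothesis, item 1, is a separate question about the population. No SUV comparison by hormone status is described, so it does not bear on this interval.

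**Conclusion.** No change to the plan follows. The SUV sentence is thin, and the 12-month review has no stated place in the analysis. Both are missing detail. Neither is an error or a contradiction.

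A one-third loss in the SUV difference needs four assumptions together: grouping by biopsy result, one value per man, exactly 3 negatives of whom one is false, and uptake in that man equal to the positives. Across 2 to 5 negatives the loss is 50% to 20% at full uptake, half that at half-way uptake, and nothing if his uptake matches the true negatives. None of these inputs is in the documents. With one value per man, any between-man contrast in 15 men has a pooled-t half-width of at least 1.12 observed SDs, so the estimate will be coarse whichever rule is used. The SUV comparison the plan does describe is exploratory, and no decision depends on it. Analysts can fill the gap sensibly when they report.
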